**Methods:**

1. Descriptive statistics for all measures at the facility level, within treatment and control arms. Potential differences in patient (age, sex, race/ethnicity) and injury characteristics will be examined using bivariate analyses by center using  $\chi^2$  tests (categorical) and t-tests (continuous).
2. ITT analysis: multi-level mixed effects Poisson regression with robust variance estimation and clustering by site to estimate the relative risk of PEGASUS implementation on TBI guideline adherence and stratified by extracranial injury, as described in Zou, et al.  
Per protocol: As with ITT, but potentially including implementation dose/fidelity as covariate and interaction with intervention.
3. Secondary analyses (Following ITT for primary analysis): Poisson regression with robust variance estimation and clustering by site to estimate separately the relative likelihood of program implementation on these outcomes: 1) in-hospital mortality; and 2) GOSE-Peds at 3 months post TBI, analyzing GOS score as a dichotomous measure (minor-moderate impairment vs major impairment-vegetative state and death).  
Multivariable Cox regression model to examine the marginal effect of PEGASUS on mortality during the 3 months post discharge, averaged over all centers.
4. Sensitivity analyses: repeated analysis on ICP monitoring patients
5. Subgroups: COVID effect and geographic effect

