### 3.1 Study Design

This study is an open-label, multicenter, phase 3, superiority, pragmatic, parallel cluster randomized controlled trial (RCT) including 16 South American hospitals to provide usual care (n=8 sites) or the PEGASUS intervention (n=8 sites). This final design resulted after two iterations: the first iteration was a parallel cluster RCT with twelve sites (6 intervention, 6 control). In response to site requests for receiving the PEGASUS Pathway intervention, a stepped wedge design was developed and approved by the sponsor. However, the final study design was again updated in August 2020 after approvals from site PIs and sponsor from a stepped-wedge design due back to a parallel cluster RCT with sixteen sites (8 intervention, 8 control) due to COVID-19 pandemic challenges.

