### **3.7 Sample Size and Power**

A sample size of 432 participants is targeted for the planned parallel cluster study, which would have 80% power to detect a 18.7% higher ICU TBI guideline adherence rate with program implementation at the site level, with a two-sided alpha of 5%, and an intraclass coefficient of 0.05. Calculations included 58.6% guideline adherence rate estimate based on prior pilot work in Argentina and assumed no change in adherence rate at control sites. The study will not be sufficiently powered for secondary outcomes of patient mortality, discharge outcomes, or three-month follow-up outcomes.

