### **3.8 Recruitment, Retention & Follow-up**

Recruitment is limited to eligible patients admitted and consented at study sites. Based on baseline recruitment levels, the target sample size of 432 is feasible with about 9 participants per site per year. This is an in-patient intervention for the first 7 days of ICU care where intervention ICU staff are trained on intervention delivery as part of their patient care. Other data will be obtained from the health records. Follow-up data collection will be attempted at three months post-admission and can be completed in-person, via telephone, or from the health record. If unable to complete follow-up by four months, the participant will be designated lost-to-follow-up, but in-hospital data will be included. There is no incentive for participation offered to patients at any stage.

[figure not shown]

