**Questions of interest:**

- 1) Does PEGASUS implementation improve guideline adherence?
- 2) Are there any imbalances between the study arms that need to be addressed?

**Study Design:** 2-arm parallel cluster RCT

**Study population:** Pediatric (<18) ICU patients with severe TBI at 16 sites

**Exposure variable(s):** Study Arm (binary)

**Outcome variable(s):** (1) TBI guideline adherence

*"The main outcome is TBI guideline adherence during first 3 days ICU stay, calculated via our previously developed TBI guideline adherence scorecard. Using patient charts, we measure presence or absence of adherence to the indicators and capture time since injury for any observed indicators, including the main protective KPIs (ventilation, nutrition, CPP). Patient guideline adherence is defined as the sum of indicators to which care was adhered divided by the number of relevant adherence indicators for a given patient. Mean adherence scores are calculated for each site individually and across all sites."*

Describe:

- (2) Extracranial injuries
- (3) Discharge GOS
- (4) Discharge survival
- (5) 3-month GOSE-Peds
- (6) 3-month mortality
- (7) KPIs?

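### The SAP asks about imbalance between arms, but its stated tests are by center and make no allowance for clustering, and it gives no rule for acting on the result

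*SAP*

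**What the plan says.** The SAP section Questions of interest has two entries. The second reads "Are there any imbalances between the study arms that need to be addressed". It is about arms, and it contemplates some action.

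Methods, item 1 is the only procedure that bears on it. It starts with "Descriptive statistics for all measures at the facility level, within treatment and control arms" and continues: "Potential differences in patient (age, sex, race/ethnicity) and injury characteristics will be examined using bivariate analyses by center using" chi-square tests for categorical and t-tests for continuous variables. For these tests it names no contrast between arms, no significance threshold and no allowance for clustering.

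Clustering is recognized elsewhere. Item 2 specifies a "multi-level mixed effects Poisson regression with robust variance estimation and clustering by site to estimate the relative risk of PEGASUS implementation" for the primary ITT analysis, and the secondary Poisson models in item 3 are also clustered by site. None of these models names a covariate, and the Cox model in item 3 is called multivariable without naming one.

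The SAP section Covariates/confounders lists patient, implementation and organizational variables. It gives no rule for which of them enter a model.

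**The concern.** The question and the method do not match. A comparison among centers says nothing direct about the two arms, and a two-sample t-test does not handle 16 groups. If the intention was to compare arms with the same tests on individual children, the tests treat children from one site as independent although the site was the unit of allocation. Their p-values are then too small.

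Looking at imbalance is legitimate here. Protocol 3.3 has site staff aware of their arm, and children are enrolled after their site has been allocated, so recruitment may differ between arms for reasons other than chance. A test that over-flags cannot separate such differences from noise.

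What is at stake is the step after the table. With no stated rule for addressing an imbalance, the flagged variables are the obvious candidates for adjustment. The covariate list includes quantities that arise after allocation: length of stay, surgery, and implementation dose and fidelity. Adjusting for any of these because it differed between arms could remove part of the intervention's effect. In an open-label trial, a covariate choice made from the data is also hard to defend.

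**Working it through.** **Inputs**
- Total 432 children: "A sample size of 432 participants is targeted for the planned parallel cluster study" (Protocol 3.7).
- 16 sites, 8 per arm (Protocol 3.1), so 432 / 16 = 27 per site. Protocol 3.8 agrees: 9 per site per year over three years is 27.
- ICC and alpha: "with a two-sided alpha of 5%, and an intraclass coefficient of 0.05" (Protocol 3.7). Both are stated for the adherence outcome. Using them for baseline variables is an assumption, because the documents give no ICC for those variables and no threshold for the imbalance tests.

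**The plan's own figure.** Take 58.6% against 58.6 + 18.7 = 77.3%, unpooled variance and a normal approximation:
- n per arm before inflation = (0.586 × 0.414 + 0.773 × 0.227) × (1.96 + 0.842)² / 0.187² = 93.8.
- Design effect = 1 + (27 − 1) × 0.05 = 2.3.
- Total = 2 × 93.8 × 2.3 ≈ 432.

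The stated 432 reproduces, so 27 per site and a design effect of 2.3 are the plan's own working values.

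**Reading 1: tests among the 16 centers.** A one-way test stands in here for the t-test, which cannot be applied to 16 groups. In 20,000 simulated trials of 16 sites × 27 children with no arm effect, it flags a variable 78% of the time at ICC 0.05. Those flags reflect real center differences. They are not false positives about the arms, and they do not answer the arm question.

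**Reading 2: tests by arm on individual children.** The true size of a nominal 5% test is 2 × [1 − Φ(1.96 / √DE)], with DE = 1 + 26 × ICC.

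| ICC | DE | True size | Multiple of 5% |
|---|---|---|---|
| 0 | 1.00 | 5.0% | 1.0 |
| 0.01 | 1.26 | 8.1% | 1.6 |
| 0.02 | 1.52 | 11.2% | 2.2 |
| 0.05 | 2.30 | 19.6% | 3.9 |
| 0.10 | 3.60 | 30.2% | 6.0 |

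The same simulation at ICC 0.05 gives 19.5% for the t-test and 19.4% for the chi-square test.

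Protocol 3.3 ranks sites into four enrollment groups, so sizes will be unequal, but no spread is given. For an assumed coefficient of variation (CV) of site size, DE = 1 + [(1 + CV²) × 27 − 1] × ICC. At ICC 0.05, CVs of 0.4, 0.6 and 0.8 give DE of 2.52, 2.79 and 3.16, and sizes of 21.7%, 24.0% and 27.1%.

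**Reading 3: t-test on the site means, 8 against 8.** The simulated size at ICC 0.05 is 5.1%, so this test is valid.

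**The case against.** The strongest reply has three parts.

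*The text may mean site-level summaries.* The sentence before speaks of facility-level statistics within arms, so the t-tests could be run on site means, and reading 3 shows that this holds its level. That is possible for continuous variables. It does not fit a chi-square test on children's categories such as sex, and the SAP does not say it. The ambiguity stands, and it is a reason to rewrite the sentence.

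*The tests are only descriptive.* Item 1 opens with descriptive statistics, and Potential products lists a descriptive table. A reader might infer from the SAP's question that the tests select the covariates, after outcomes have been seen. The documents say neither: no rule links a test result to a model, and no timing is given. What stands is narrower. The SAP contemplates addressing imbalance and offers no other way to decide how.

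*The primary result is untouched.* This is right for the ITT model as written, which is clustered and names no covariates. It also limits the weight of the covariate list: implementation dose and fidelity have a stated possible use in the per-protocol analysis, so their presence there does not show that they would enter the ITT model.

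Two stronger numerical readings should also be resisted. Fourfold inflation is not a ceiling and not a certainty: it belongs to reading 2 at one borrowed ICC, and the table runs from 1.6 to 6.0 times for ICC 0.01 to 0.10. One could also compute 1 − (1 − 0.196)⁵ = 66% for at least one false flag among five variables. That needs five independent variables, the borrowed ICC and a 5% threshold, none of which the SAP supplies.

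**Conclusion.** The point holds as a fault in item 1. As specified, the tests do not validly answer the SAP's own second question. Read literally, they compare the wrong groups; run by arm on individual children, they have the wrong error rate, about 20% instead of 5% at ICC 0.05 with 27 per site. The range is 8% to 30% for an assumed ICC of 0.01 to 0.10 with equal sites, and higher with unequal ones. These two faults are alternatives and do not add up, because the inflation applies only to the by-arm reading.

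The size rests on the adherence ICC or the assumed range, on equal site sizes unless stated, and on a 5% threshold. The documents do not support saying that the primary analysis is invalid. It is affected only if covariates are added on the strength of these tests, which the SAP neither plans nor rules out.

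**What to change.** In Methods, item 1, replace the by-center chi-square and t-tests with summaries by arm and by site, and give standardized differences between arms without p-values. If a test is kept, make it cluster-level (for example, on the 16 site means or proportions) or cluster-adjusted.

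Name the covariates of any adjusted model in advance, including the Cox model, and state that they will not be chosen from observed imbalance. Suitable candidates are:
- the enrollment-group strata used in the randomization;
- each site's adherence in the baseline period;
- admission characteristics that the intervention cannot affect, such as age, sex, injury severity and first CT findings.

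The children analyzed are enrolled after their site was allocated, so the criterion for a child-level variable should be that the intervention cannot affect it, not that it was measured before randomization. Length of stay, surgery, dose and fidelity should be kept out of adjusted ITT models.

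The cost is a change of SAP wording and the loss of baseline p-values. No new data are needed.

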### 3.3 Site Randomization Plan

Sixteen study sites were recruited by CIIC based on willingness to participate and annual severe TBI admissions. Sites were added after the original proposal to increase the potential patient recruitment population. All sites receive compensation for data submission. Prior to randomization on July 13, 2020, three sites who had no or one enrolled patient during ten months of baseline usual care data collection were removed from the pool. The remaining sixteen sites participating were ranked by median monthly baseline enrollment, number of zero recruiting months, and total number of recruited patients and divided into four groups (Group A=highest enrollment group, Group D=lowest enrollment group). The study statistician performed computer block randomization within each group to assign to control and intervention arms at a 1:1 ratio. Participant assignment was dependent on the intervention or control arm assignment of the study hospital to which they were admitted.

Due to the nature of the intervention study team, site staff, and patients' families are aware of the site's arm assignment.

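### The primary test takes its variance from 16 sites, names no small-sample method and leaves out the randomisation groups, so the 5% level is not secured in either direction

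*SAP*

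**What the plan says.** SAP, Methods, item 2 (ITT analysis) specifies a "multi-level mixed effects Poisson regression with robust variance estimation and clustering by site to estimate the relative risk" and refers to a cited methods paper. It names no small-sample correction, degrees of freedom, reference distribution or permutation test, and the protocol does not either.

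Protocol 3.1 sets the number of clusters: "including 16 South American hospitals to provide usual care (n=8 sites) or the PEGASUS intervention (n=8 sites". Protocol 3.3 describes restricted randomisation. Sites were ranked on baseline enrolment and "divided into four groups (Group A=highest enrollment group, Group D=lowest enrollment group"; then "The study statistician performed computer block randomization within each group to assign to control and intervention arms at a 1:1 ratio". Group sizes are not given. The groups appear neither in the SAP model nor in its covariate list. The nearest listed item is annual trauma volume, among the organisational covariates, and Methods does not say whether any listed covariate enters the primary model.

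Protocol 3.7 fixes the error rate, "with a two-sided alpha of 5%, and an intraclass coefficient of 0.05".

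**The concern.** A cluster-robust (sandwich) variance is reliable when there are many clusters. With 8 per arm it tends to be too small, and it is itself estimated on about 14 degrees of freedom. A normal reference ignores both facts. Leaving out the randomisation groups works the other way. If the groups predict adherence, balancing them makes the arm difference more precise than an unadjusted variance recognises, and the test becomes conservative.

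The plan therefore states a 5% level for its one primary comparison and leaves open the choices that decide whether 5% is achieved. Defensible options give different p-values and intervals from the same data, so the choice should be made before the arms are compared.

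**Working it through.** **Inputs from the documents.** 16 sites, 8 per arm (Protocol 3.1). 432 patients, ICC 0.05, adherence 58.6%, difference 18.7, alpha 5% two-sided, power 80% (Protocol 3.7). Mean site size 432/16 = 27, which agrees with "the target sample size of 432 is feasible with about 9 participants per site per year" over three years (9 × 3 = 27).

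**Assumed, because the documents do not give them.** Normal reference; site-size CV; share of between-site variance explained by the groups; score SD 0.15-0.25; four groups of four sites.

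**1. The plan's own figure.** Reading 18.7 as percentage points (58.6% to 77.3%):
- Design effect = 1 + 26 × 0.05 = 2.3.
- Unpooled variance sum = 0.586 × 0.414 + 0.773 × 0.227 = 0.4181.
- n per arm = (1.960 + 0.842)² × 0.4181 / 0.187² = 93.84.
- Total = 93.84 × 2.3 × 2 = 431.7, i.e. 432.

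So 432 reproduces, using normal quantiles with no allowance for 16 clusters. The standard error is √(0.4181 × 2.3 / 216) = 0.0667, and 0.187/0.0667 = 2.80. Power is 80.0% with a normal reference, 74.1% with t(14) and 72.3% with t(11).

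**2. Equal sites, groups not prognostic, arm-only model (exact).** The rejection rate is P(|t14| > 1.96√f), where f is the expected ratio of the sandwich to the true variance. The interval factor is (2.145/1.960)/√f.

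| Sandwich scaling | f | Rejection rate | Correct t(14) interval is wider by |
|---|---|---|---|
| none | 7/8 | 8.8% | 17% |
| 16/15 | 14/15 | 7.9% | 13% |
| 16/14 | 1 | 7.0% | 9% |

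**3. Unequal sites or prognostic groups (null simulation, normal reference, the same three scalings).**

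| Scenario | Rejection rate |
|---|---|
| Groups not prognostic, CV 0.4-0.7 | about 8-12% |
| Groups explain 30% of between-site variance | about 4-10% |
| Groups explain 60% | about 2-7% |
| Groups explain 90% | about 1-4% |

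The last three rows span equal and unequal sites and depend on how the group effect is modelled. A separate set of runs at shares of 70-90% gave 0.8-2.5% with equal sites and 1.2-5.4% with unequal sites.

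**4. Adding the groups and keeping a normal reference.** Residual degrees of freedom are 16 − 1 − 1 − 3 = 11. With equal sites the exact rate is P(|t11| > 1.96√(11/m)):
- m = 16, 15, 14 (scalings none, 16/15, 16/14): 13.2%, 12.1%, 11.0%.
- m = 11 (the matching 16/11 scaling): 7.6%.

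Across the unequal-site scenarios the ranges are about 11-17% with the first three scalings and about 7-10% with 16/11.

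**5. Does the random intercept rescue the test?** For the fraction outcome, the variance of a site mean is SD² × 2.3/27, which is 0.0019 at SD 0.15 and 0.0053 at SD 0.25. The Poisson model already assumes 0.586/27 = 0.0217. The data look under-dispersed to the model, so the fitted site variance tends to zero and inference falls back on the sandwich. In fitted mixed Poisson models with a yes/no outcome, the site variance was zero in about 66-82% of runs, and rejection rates were similar to those above.

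**6. A group-respecting alternative.** Site means analysed with arm and group on t(11) rejected about 4.3-5.4% in every scenario tried.

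**The case against.** The strongest reply is that the SAP does not state a normal reference. It points to a methods paper that is not available here, and the analyst might use a t reference or a correction as a matter of course. That stands. A reader might infer that the planned test has a 7-12% error rate, but the documents do not support this. Those rates follow only from a normal reference combined with groups that do not predict adherence.

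A reader might also infer that the interval is too narrow. That too is conditional: with prognostic groups it can be too wide. The documents say nothing on whether enrolment rank predicts adherence, so the direction is unknown.

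The site-size CV is unknown as well. Protocol 3.3 says that "three sites who had no or one enrolled patient during ten months of baseline usual care data collection were removed from the pool". At 9 patients per year a site expects 7.5 in ten months, and 0 or 1 then has probability e^(−7.5) × 8.5 = 0.5%. Three such sites among 19 would be very unlikely with equal rates. But sites were added after the original proposal and the period ran into COVID-19, so this hints at unequal sizes and does not establish a CV. The excess in step 2 does not depend on it.

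It may be said that adding the groups is dangerous in itself. Most of the rise to 11-17% comes from a sandwich not scaled for five parameters. With the 16/11 scaling the cost is modest, but the test still does not hold 5%.

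Finally, at the design effect little changes. For the fraction at SD 0.25 the standard error is 0.25√(2 × 2.3/216) = 0.0365, and power at 18.7 points is 99.9% (normal), 99.7% (t14) and 99.6% (t11). This stands for a large effect. It does not help with a null or small effect, or with interval width.

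**Conclusion.** The point holds as under-specification with a measurable consequence. The primary inference rests on 16 sites, no small-sample method is named, and the groups that constrained the randomisation are ignored. If run with a normal reference, the analysis does not hold the stated 5% level. It rejects 7.0-8.8% with equal sites and non-prognostic groups (exact), about 8-12% at CV 0.4-0.7, and as little as about 1-4% if the groups explain 90% of between-site variance. Only the equal-site figures are free of an assumed CV, and all of the rates assume the normal reference. This should be fixed. It does not show that the trial's conclusion at the planned effect would be wrong.

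**What to change.** Before the arms are compared, amend SAP Methods item 2 so that the primary p-value and confidence interval come from one pre-named method. Either of these would do:

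1. A permutation test over the allocations possible within the four groups, with the interval by test inversion on the log ratio. This keeps the planned patient-weighted ratio. With four sites per group there are 6⁴ = 1,296 allocations; the actual group sizes should be stated.
2. A site-level analysis with arm and group on t(11). The SAP already plans the inputs: "Mean adherence scores are calculated for each site individually and across all sites". State that it weights sites equally, which is a different weighting from the Poisson model. Analyse log site means if a ratio and its interval are to be reported.

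Also state whether the organisational covariates enter the model, and reduce the degrees of freedom if they do. Use a small-sample correction for the robust Poisson analyses of in-hospital mortality and 3-month GOSE-Peds.

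The cost is a few SAP lines, standard software and a wider interval. Protocol 3.7 should restate power, which on its own inputs falls from 80.0% to 74.1% (t14) or 72.3% (t11), before any precision gained from the groups. For the fraction at SD 0.25 and equal sites, the difference detectable with 80% power moves from 10.2 points to 11.0 (t14) or 11.2 (t11).

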**PEGASUS Participant Timeline**

## CHAPTER 4. INTERVENTION

The PEGASUS program intervention has multi-level components to increase TBI guideline adherence. It will be implemented from October 2020-September 2023. The patient level clinical care pathway is implemented for each eligible, consented patient at an intervention site for up to seven days of their ICU stay. Intervention site care providers supply perspectives and knowledge elements quarterly. At the hospital level, intervention sites participate in quarterly focus groups, morbidity and mortality case reviews and quality improvement efforts, and regular motivational interviewing informed (MI) check-ins with site PIs facilitated by CIIC.

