## 4.4 PEGASUS Pathway

[figure not shown]
The PEGASUS pathway does not prescribe specific drug doses or treatments but provides guidelines that inform the clinical assessment and treatment for individual patients. The PEGASUS program has been iteratively refined for use in the South American context and includes additional nursing resources for rounding and family education guides to encourage engagement.

As a pragmatic implementation science study with quality improvement efforts, the components of the study are designed to be adaptable to support sites' needs and to evaluate process measures to address reach (number of patients), dose (% processes implemented), and fidelity (variance from recommended

processes and timely clinical pathway adoption). The Theoretical Domain Framework (TDF) and the Determinants of Implementation Behavior Questionnaire (DIBQ) guide these efforts.

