#### 8.4 Data Collection Timeline

Baseline data collection will occur at all participating sites from September 2019-September 2020. From October 2020-September 2023, intervention sites will collect additional data associated with the intervention implementation. The Data Collection Timeline below shows the data types collected (leftmost column) and the intervals of repeated measures.

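### The SAP's per-protocol model adds an arm-by-dose interaction that cannot be estimated when dose exists only at intervention sites, and dose has no stated measurement window.

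*SAP*

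**What the plan says.** The SAP (Methods, item 2) gives the per-protocol analysis one sentence. It is the ITT model, a multi-level Poisson regression with robust variance and clustering by site, "potentially including implementation dose/fidelity as covariate and interaction with intervention". No per-protocol population, exclusion rule or threshold of delivery is given.

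The protocol (section 4.4) defines the process measures as "dose (% processes implemented), and fidelity (variance from recommended" processes, with timely adoption of the pathway also counted under fidelity. The SAP's covariate list says that reach, dose and fidelity come from medical records, and does not say in which arm or over what period.

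On where these data arise, section 8.4 says that from October 2020 to September 2023 "intervention sites will collect additional data associated with the intervention implementation". Chapter 4 has the pathway delivered to consented patients at intervention sites "for up to seven days of their ICU stay", alongside hospital-level activities (focus groups, case reviews, check-ins) at those sites. Section 3.5 has control participants agreeing to record abstraction only.

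The outcome in the SAP is "TBI guideline adherence during first 3 days ICU stay".

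**The concern.** An interaction between arm and dose asks whether the effect of dose differs between arms. That requires dose to vary in both arms. If usual-care sites deliver no PEGASUS processes, their dose is either zero by construction or undefined, and the question has no answer.

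The label adds to the problem. A reader who sees a per-protocol relative risk expects the effect of the program when delivered as intended. With dose in the model and controls at zero, the arm coefficient is instead the effect of belonging to an intervention site that delivered nothing. If PEGASUS works through the processes it delivers, that coefficient tends towards no effect even when the program succeeds, and it could be published as a null per-protocol result.

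Timing is a second, smaller matter. The pathway may run past the close of the outcome, and nothing in the plan stops later processes from being counted in the dose used to explain that outcome.

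**Working it through.** **The plan's own sample size first.** Inputs from protocol section 3.7: "A sample size of 432 participants is targeted for the planned parallel cluster study"; "80% power to detect a 18.7% higher ICU TBI guideline adherence rate"; "with a two-sided alpha of 5%, and an intraclass coefficient of 0.05"; control adherence 58.6%. Section 3.1 gives 8 sites per arm.

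- Mean site size: 432 / 16 = 27. Design effect: 1 + (27 − 1) × 0.05 = 2.30.
- With 18.7 as percentage points, intervention adherence is 58.6% + 18.7% = 77.3%.
- Per arm before clustering: (1.960 + 0.842)² × (0.586 × 0.414 + 0.773 × 0.227) / 0.187² = 93.84.
- Total: 93.84 × 2.30 × 2 = 431.7, which rounds up to 432.

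The figure reproduces. The planned effect as a relative risk is 77.3 / 58.6 = 1.32. Reading 18.7% as relative (58.6% to 69.6%) would need about 1,380 participants, so that reading does not fit. Nothing below changes the 432.

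**The per-protocol model.** Let A be arm (0 or 1), D dose and μ expected adherence. As written:

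log μ = b0 + b1·A + b2·D + b3·A·D

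The rank of the fixed-effect columns [1, A, D, A·D] was checked on 16 sites × 27 patients, with D drawn uniformly between 0.3 and 1 where it exists. These dose values are an assumption. Where dose exists only in the intervention arm, the ranks hold for any values that vary within that arm. The site random effect does not alter the fixed-effect columns.

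| Treatment of dose in controls | Patients used | Rank of [1, A, D, A·D] | What is lost |
|---|---|---|---|
| Coded 0, dose at patient level | 432 | 3 of 4 | separate interaction |
| Coded 0, dose at site level | 432 | 3 of 4 | separate interaction |
| Missing, complete cases | 216 | 2 of 4 | arm effect and interaction |
| Measured and varying in both arms | 432 | 4 of 4 | nothing |

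**Coded 0.** When A = 0, D = 0, so A·D = D for every patient and the model collapses to

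log μ = b0 + b1·A + (b2 + b3)·D

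Only the sum b2 + b3 can be estimated. It is the dose slope within the intervention arm. The coefficient b1 is the log relative risk of an intervention site at D = 0 against control. If benefit is proportional to dose, log μ = b0 + g·D, then b1 = 0 and its relative risk is 1.0, whatever the ITT relative risk.

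**Missing.** The 8 × 27 = 216 remaining patients all have A = 1, so A duplicates the intercept and A·D duplicates D.

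**Measured in both arms.** The interaction is estimable, but the candidate measure is chart-abstracted departure from recommended care. The outcome is itself chart-abstracted adherence to guideline indicators, so the regression would partly have the outcome on both sides.

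**Timing.** The outcome closes at ICU day 3, the pathway may run to day 7, and dose has no stated window. The 7-day limit in the SAP's covariate list is attached to patient case-report data. Implementation measures are a separate item.

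**The case against.** The case on the other side has real content.

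- **The model is optional.** The SAP says only that the terms may be included. True, but they are all that separates this analysis from ITT. Without them the per-protocol analysis is ITT under another name, and the choice is left open until data are in hand.
- **Dose might exist in controls.** The SAP draws dose and fidelity from medical records, and control sites supply records. No sentence restricts dose to one arm, and the data-collection timeline figure is not available to check. This stands as a limit: the restriction is a strong inference. For fidelity, an estimable interaction is possible, at the price of overlap with the outcome.
- **The model would still fit.** Software commonly drops the redundant column, and [1, A, D] has full rank 3. The contrast with control at a delivered dose d, b1 + (b2 + b3)·d on the log scale, is then estimable. This also stands. The misleading number is the uncentred arm coefficient, so a contrast at a stated dose need not be banned. It is not randomised, because delivered dose is not assigned.

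Two stronger readings are tempting. A reader might infer that dose accrued over 7 days will be used to explain a 3-day outcome, with 4 of the 7 pathway days falling too late. The documents do not support this: they give the pathway's duration, not a window for dose, and part of dose may be hospital-level with no patient-day clock. A reader might also infer that this is the trial's only look at delivered intensity. It is not: the SAP plans a figure of dose/fidelity variation, and Aim 1b covers implementation factors.

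**Conclusion.** The point holds for a secondary analysis. Followed literally, the per-protocol model includes an interaction that cannot be separated from the dose slope (rank 3 of 4 with controls at zero), or it loses every control site (216 intervention patients left, rank 2 of 4). In the first case the arm coefficient is a zero-dose contrast, which is not a per-protocol effect.

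This rests on dose being generated only at intervention sites, inferred from protocol sections 3.5, 4.4 and 8.4 and Chapter 4, and on dose varying among intervention patients or sites. The relative risk of 1.0 for the arm coefficient rests further on benefit being proportional to dose, and is an illustration rather than a forecast. On timing, the supportable statement is that the window is undefined, so patient-level dose from after day 3 could enter.

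The defect should be corrected before analysis. The primary ITT comparison and the sample size do not depend on it.

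**What to change.** Replace the per-protocol sentence in SAP Methods item 2 with text to this effect:

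> Dose-response is examined within the 8 intervention sites only, as an exploratory analysis, with no arm term and no arm-by-dose or arm-by-fidelity interaction. Patient-level dose is the share of PEGASUS processes delivered up to the end of ICU day 3. Site-level dose (case reviews, focus groups, check-ins) counts only activity before that child's admission. If a contrast with control is also shown, it is reported at a stated delivered dose, not as the uncentred arm coefficient, and is described as non-randomised.

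Remove the per-protocol label. Define dose and fidelity once: level (patient or site), the arm or arms in which each is recorded, how controls are coded if they appear in any model, and which fidelity items overlap with the adherence scorecard.

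The cost is SAP wording only. The downside is that the dose analysis becomes openly an 8-site exploratory analysis with low precision.
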